## **Scientific Aims: Determine the effects of NR on skeletal muscle oxidative phosphorylation capacity in heart failure:**

- A) Baseline, 12-week ( $\pm 5$ -days) (on NR) and 16-week ( $\pm 5$ -days) (4-week washout) skeletal muscle fixed-load sub-maximal exercise NMR spectroscopy to assay skeletal muscle phosphocreatine recovery time as a measure of mitochondrial oxidative phosphorylation.
- B) Baseline and 12-week ( $\pm 5$ -days) cardiopulmonary testing to assay VO2max and anaerobic thresholds.
- C) Baseline and 12-week ( $\pm 5$ -days) serum quantitative metabolomic profiling, pre- and post-CPET to evaluate whether NR increases the rate of oxidative phosphorylation.
- D) Baseline and 12-week ( $\pm 5$ -days) quantitative serum cytokine immunoassay profiling to assess whether NR blunts HF linked inflammation.
- E) Skin biopsy at baseline and research blood at baseline and 12 weeks ( $\pm 5$ -days) to explore the effects of NR on oxidative phosphorylation and inflammation in respective subject primary skin fibroblasts.

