### 3. Study Design and Procedures

The study design is an open label pilot study with subjects serving as their own controls. The outline of the clinical protocol is shown in a tabular schematic below.

Visit #	1	2	3	4	5	6	7A/B	8	9
Weeks	-1 to -3	0	0+ 1-2 days	2	4	6	12	12 + 1-2 days	16
Procedures									
History	X	X		X	X	X	X		X
Physical exam	X			X	X	X	X		X
Initiate NR/dispense meds			X						
Dose adjustment				X 	X 	X 			
Stop NR								X	
Urine pregnancy test	X 	X 	X 				X 	X 	X 
Clinical blood tests	(X)	X 	X 	X	X	X	X 	X 	X
NMR spectroscopy		X 	X 				X 	X 	X
CPET		X 	X 				X 	X 	
Echo	X*						X		
Research blood		X 	X 					X 	
Skin biopsy		X 	X 						
AE assessment				X	X	X	X	X	X
Concomitant meds/tx	X			X	X	X	X	X	X
Study drug adherence				X	X	X	X		
Key:									
(X) Performed only if baseline laboratory studies not performed during routine testing within 6 months									
X Procedure performed									
 Increase NR dose by 250mg BID									
 Pregnancy test will only be performed in women with childbearing potential. It can be completed at Visit 1, 2 and/or 3 and Visit 7 or 8									
 Skin biopsy will be completed at either Visit 2 or 3.									
 NMR spectroscopy, clinical and research blood, and CPET testing can be performed at either Visit 2 or 3 for baseline timepoint and Visit 7 or 8 for end of treatment timepoint.									
* Procedure is optional (Echo is optional on Visit 1 if PI feels there is an adequate and timely historical Echo)									
Visits 1, 4, 5, 6, and 7 may take place at either WRNMMC or NIH Clinical Center.									
Visits 2, 3, 7B, 8, and 9 will take place at the NIH Clinical Center									

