### **Visit 2 (Week 0, NIH)**

#### **The following procedures will be performed at Visit 2:**

- Brief history to review heart failure symptoms
- NIH consent
- Blood draws will analyze: CBC+Diff, BNP, HbA1C, uric acid, ALT, CK, Chemistry panel (electrolytes, glucose, blood urea nitrogen and creatinine) and insulin levels. This blood draw will not be performed if subject has normal clinical blood work within the last two weeks.
- Baseline skeletal muscle exercise NMR Spectroscopy
- Urine pregnancy test for women with childbearing potential
- Skin biopsy will be done at Visit 2 or Visit 3

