### **Visit 3 (Week 0 + 1-2 days, NIH CC)**

#### **The following procedures will be performed at Visit 3:**

- Dispense NR: Level 1 ( 250mg PO BID to initiate supplementation in evening after visit 3).
- Dispense Level 2-4 bottles of NR: Level 2 (500mg PO BID – to initiate after visit 4), Level 3 (750mg PO BID – to initiate after visit 5) and Level 4 (1000mg PO BID – to initiate after visit 6 and maintain through visit 7).

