### **Cytokine profiling:**

Circulating cytokine levels have been found to directly correlate with worsening functional capacity in heart failure patients and have been shown to have prognostic value as a biomarker. Emerging evidence additionally supports that exercise training and NR reduce cytokine production. Taken together, we would propose that NR supplementation may similarly reduce circulating cytokine production. To investigate this, serum samples from subjects will be collected at baseline and in response to peak exercise during the CPET procedure pre- and post-NR supplementation. Cytokine, chemokine and acute phase reactants will be quantified using the Luminex bead based multiplexing assay to measure  $\approx$  40 analytes simultaneously using the NIH Center for Human Immunology standardized protocols.

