### **Skin biopsy:**

A recent study has shown that human primary fibroblasts incubated with serum from individuals, pre- and post-exercise, showed an upregulation of mitochondrial regulatory genes following exercise. We will employ this same approach using serum obtained from study subjects pre- and post NR administration. A single 3mm or less skin biopsy sample would be obtained at the beginning of the study. The assessment of mitochondrial oxidative phosphorylation in primary skin fibroblasts conditioned with serum from heart failure subjects pre- and post-NR would validate and augment the data acquired by NRM spectroscopy.

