- **Skin biopsy:** This procedure is performed using local anesthetic. After washing the skin with alcohol and numbing the skin, a 4 mm or smaller circle of skin is removed steriley and the wound is dressed. The entire procedure takes approximately 5 minutes. Discomfort at the biopsy site is usually mild and transient. This can be treated with minor analgesics. Normally, the risks include a reaction to the local anesthetic and the slight possibilities of local bleeding or infection. Scarring always occurs at the biopsy site.
- **MR Spectroscopy:**

MRI uses non-ionizing radiation and is safe when used on subjects that are appropriately screened for the procedure. Subjects with any exclusionary criteria (Pregnancy, Aneurysm clip, implanted devices such as neural stimulators, cardiac pacemaker, defibrillator, cochlear implant, foreign body, such as, metal shavings, or insulin pumps, will be excluded from the study.

Potential risks of MRI relate to effects of the main, static magnetic field, the applied radiofrequency (RF) power, and the rapidly switching magnetic field gradients. The risks associated with each of these are described below. We will stay within all the FDA guidelines for the applied RF power, the rate of switching magnetic fields and the noise levels that these switching gradients produce (see Guidance for Magnetic Resonance Diagnostic Devices – Criteria for Significant Risk Investigations, issued July 14, 2003. <http://www.fda.gov/cdrh/ode/guidance/793.pdf>).

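### The schedule lets the only skin biopsy precede the baseline research blood, so a baseline-only wound response cannot be ruled out as a cause of a later fall in inflammatory markers

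*Combined protocol and SAP*

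**What the plan says.** Two notes to the schedule in Section 3 govern the baseline procedures. Note 3 reads "Skin biopsy will be completed at either Visit 2 or 3". Note 4 reads "NMR spectroscopy, clinical and research blood, and CPET testing can be performed at either Visit 2 or 3 for baseline timepoint". The Visit 2 list repeats that "Skin biopsy will be done at Visit 2 or Visit 3". The list shared by Visits 2 and 3 contains the CPET, the research blood and the biopsy. Visit 3 is 1-2 days after Visit 2, and both take place at the NIH Clinical Center.

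Section 5 (Skin biopsy) states that "A single 3mm or less skin biopsy sample would be obtained at the beginning of the study", so there is none at week 12. Section 5 ties the metabolite and cytokine serum to the CPET. On the cytokine panel it says that "Cytokine, chemokine and acute phase reactants will be quantified".

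Aim D is "quantitative serum cytokine immunoassay profiling to assess whether NR blunts HF linked inflammation", comparing 12 weeks with baseline. Section 8 lists it among the additional analyses and names no test for it. The design is open label, with each subject as his or her own control.

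**The concern.** Aim D counts a fall from baseline to week 12 as evidence that NR reduces inflammation. Anything that raises inflammatory analytes at baseline but not at week 12 gives the same picture. A biopsy shortly before the baseline sample is one candidate, since the panel includes acute phase reactants and the biopsy happens only once.

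Nothing else in the design would expose such an artefact. There is no control arm, and no cytokine measurement is planned at the week-16 washout visit. Aim C (metabolites) and Aim E (fibroblasts conditioned with subjects' serum) also rely on the baseline research blood and would share the asymmetry.

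**Working it through.** **1. Which orders does the plan permit?** Notes 3 and 4 are independent, which gives four combinations:

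| Biopsy | Research blood and CPET | Biopsy before blood? |
|---|---|---|
| Visit 2 | Visit 3 | Yes, by 1-2 days |
| Visit 2 | Visit 2 | Possible; order within the day not stated |
| Visit 3 | Visit 3 | Possible; order within the day not stated |
| Visit 3 | Visit 2 | No |

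Only the last combination guarantees an undisturbed baseline. The first is a natural reading of the visit lists: the Visit 2 list names NMR spectroscopy and the biopsy, but neither CPET nor research blood. The shared list puts research blood above the biopsy, but as an inventory and not a sequence.

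**2. What size does the plan give?** None. Section 11 (Risks and Discomforts) describes local and usually mild effects. Any figure below is therefore an assumption.

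**3. The sample size used for the illustration.** The plan's 15 completers come from the primary endpoint, with a difference of 4.8 sec and an SD of 6.6 sec. By the normal approximation, n = (SD × (z0.975 + z0.80) / difference)² = (6.6 × 2.8016 / 4.8)² = 14.84, rounded up to 15. The figure reproduces on that basis. The plan gives no power calculation for Aim D; 15 is borrowed only as the number of pairs.

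**4. Bias in the mean change.** Let f be the share of subjects biopsied before the blood, and s the resulting rise in their baseline, in SDs of the paired difference. With no NR effect,

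bias in (week 12 minus baseline) = −f × s.

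For example, f = 0.5 and s = 0.25 give −0.125 SD. If f = 0 or s = 0, the bias is zero.

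**5. Chance of a spurious significant fall in one analyte.** This was simulated with 20,000 runs per cell, 15 pairs, normally distributed differences and no NR effect. The test is the exact two-sided Wilcoxon signed rank test at 0.05, borrowed from the primary analysis, counting falls only. The nominal one-directional rate is 2.5%.

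| f | s = 0.1 | s = 0.25 | s = 0.5 | s = 1.0 |
|---|---|---|---|---|
| 25% | 2.8% | 3.8% | 6.0% | 11.7% |
| 50% | 3.7% | 5.9% | 13.2% | 34.9% |
| 100% | 5.2% | 13.8% | 41.8% | 93.7% |

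The range for s, from 0 to 1 SD, is assumed, and the upper end should not be read as likely. The table shows only how sensitive a comparison of this size is to a baseline shift. Drawing the blood first in every subject sets f to zero and returns the rate to its nominal level.

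**The case against.** The strongest objection is that no mechanism is shown. The documents do not say that so small a biopsy changes any circulating marker, and they describe its effects as local. This stands: the bias is possible, not demonstrated.

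A reader might infer that the biopsy can only raise inflammatory markers and so pushes Aim D towards benefit. The documents do not support that for a panel of about 40 analytes. Section 11 also mentions minor analgesics after the biopsy, another baseline-only exposure whose direction is not stated. For metabolites and for the fibroblast readouts, no direction can be given.

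A reader might also infer that about half of the subjects would be affected. That needs an even choice of biopsy visit with blood always at Visit 3, and neither is stated. One centre performs both visits, and the true share could be zero.

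Two further points limit the damage. Samples are taken at rest and after exercise in the same session, so a constant additive offset would cancel from the exercise response; only comparisons of absolute levels remain exposed. And if both times are recorded, subjects biopsied first can be identified, although an analysis without them would be imprecise with about 15 completers.

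Finally, an uncontrolled change in cytokines could not be firmly attributed to NR even with perfect ordering. That is true, but it is no reason to leave in place an alternative explanation that can be removed at almost no cost.

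**Conclusion.** The gap in the schedule is certain; its effect is not. The plan permits the biopsy before the baseline research blood, and no biopsy precedes the week-12 blood. A baseline-only wound response therefore cannot be ruled out as a cause of a fall in inflammatory analytes under Aim D. Aims C and E share the exposure with unknown direction. The size runs from zero to an amount that the documents do not allow anyone to bound.

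It would be wrong to conclude that the trial's main result is at risk. The primary endpoint is phosphocreatine recovery time by NMR spectroscopy and does not use this blood. This is a minor point about additional analyses in a pilot, worth acting on because the remedy is simple.

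**What to change.** In schedule notes 3 and 4, the Visit 2 list and the list shared by Visits 2 and 3, state that the skin biopsy is done only after the baseline research blood, both before and after the CPET, has been drawn. It can be the last procedure of that visit or be done at the later visit. Record the time of the biopsy and of each research draw. In Section 8, add a sensitivity analysis that flags any subject with the reverse order.

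This fits the existing visits. The biopsy serves to supply fibroblasts, nothing in the documents requires it before the blood, and NR starts only in the evening after Visit 3, so the biopsy still precedes the first dose. No visit, sample or procedure is added. The only loss is some flexibility: when the CPET falls at Visit 3, the biopsy must follow it that day.

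Separately, Section 5 gives the biopsy as 3 mm or less, whereas Section 11 has "a 4 mm or smaller circle of skin is removed steriley". The two statements must be reconciled.

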#### **The following procedures will be performed at either Visit 2 or Visit 3:**

- Baseline Cardio-Pulmonary Exercise Testing
- Research Bloods
- Skin biopsy
- Blood draws will analyze: CBC+Diff, proBNP, HbA1C, uric acid, ALT, CK, Chemistry panel (electrolytes, glucose, blood urea nitrogen and creatinine) and insulin levels. This blood draw is not required if subject has normal clinical blood work within the last three weeks.
- Baseline skeletal muscle exercise NMR Spectroscopy
- Urine pregnancy test for women with childbearing potential

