## **Visit 7 (Week 12, WRNMMC and/or NIH CC)**

**The following procedures will be performed at the follow-up visit (Day 84 ± 5):**

- 7A WRNMMC (Day 84 +/-5) Medical history, physical examination, current medical treatments
- Blood draws will analyze: CBC+Diff, proBNP, HbA1C, uric acid, ALT, CK, Chemistry panel (electrolytes, glucose, blood urea nitrogen and creatinine) and insulin levels.
- Record of adverse events, if any
- Study drug adherence with pill count
- Record of concomitant medications or interventions, if any
- Continue Level 4 NR - 1000mg PO BID
- Echocardiography

7B NIH (Day 84+/-5)

- Pregnancy test on women with childbearing potential (may be performed at Visit 7 or 8)

- Skeletal muscle exercise NMR spectroscopy or CPET
- Research blood if CPET performed at this visit

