### **Visit 8 (Visit 7B + 1-3 days, NIH CC)**

- CPET or Skeletal muscle exercise NMR spectroscopy (whichever was not done at Visit 7B)
- Research blood if CPET performed at this visit
- Pregnancy test on women with childbearing potential (may be performed at Visit 7 or 8)
- Record of adverse events, if any
- Study drug adherence with pill count
- Discontinue NR
- Record of concomitant medications or interventions, if any

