### **Visit 9 (Week 16 ± 1 week, NIH)**

The following procedures will be performed at the final study visit (Day 112 ± 5)

- Medical history, physical examination, current medical treatments
- Blood draws will analyze: CBC+Diff, proBNP, HbA1C, uric acid, ALT, CK, Chemistry panel (electrolytes, glucose, blood urea nitrogen and creatinine) and insulin levels.
- Pregnancy test on women with childbearing potential
- Record of adverse events, if any
- Record of concomitant medications or interventions, if any
- Skeletal muscle exercise NMR spectroscopy

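### The order and spacing of the MRS scan and the maximal exercise test are not held the same at baseline and week 12, so any carry-over from the exercise test would enter the uncontrolled primary change (minor, cheap to fix)

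*Combined protocol and SAP*

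**What the plan says.** Section 3, note 4 to the schedule table, says "NMR spectroscopy, clinical and research blood, and CPET testing can be performed at either Visit 2 or 3 for baseline timepoint", and gives the same choice between Visits 7 and 8 at the end of treatment.

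The visit descriptions keep the choice open:

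- **Baseline.** The Visit 2 list includes "Baseline skeletal muscle exercise NMR Spectroscopy" and does not list CPET. A further list, headed "The following procedures will be performed at either Visit 2 or Visit 3", contains both tests. Nothing bars doing both at one visit.
- **Week 12.** Visit 7B has "Skeletal muscle exercise NMR spectroscopy or CPET", and Visit 8 has "CPET or Skeletal muscle exercise NMR spectroscopy (whichever was not done at Visit 7B". The two tests are therefore on separate visits, in either order. Visit 7B also carries "Research blood if CPET performed at this visit", so CPET first is clearly foreseen.
- **Spacing.** The table puts Visit 3 one to two days after Visit 2, and Visit 8 one to two days after week 12. The Visit 8 heading gives one to three days after Visit 7B.
- **Week 16.** Visit 9 has an MRS scan and no CPET.

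Section 5 describes CPET as symptom-limited. The MRS and CPET descriptions there set no order, no minimum interval and no matching. Section 8 makes the baseline to week-12 change in recovery time the primary outcome, tested by the Wilcoxon signed rank test. Section 3 states that the study is open label, with subjects as their own controls.

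**The concern.** The endpoint measures how fast leg muscle recovers its phosphocreatine after exercise, and one of the other study procedures is exercise to the limit of symptoms. If a recent CPET altered the scan, a subject scanned before CPET at one time point and after it at the other would carry that difference into the paired change. The same holds for a subject who has CPET first both times but is scanned the same day at baseline and one to three days later at week 12. With no control arm, nothing else in the design would remove the difference. The protocol also does not ask for the order and times to be recorded for this purpose, so a later check might not be possible.

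The stake is loss of power if CPET lengthens recovery and follow-on scans are more common at week 12. If the sign or the direction of the imbalance is reversed, the stake is a spurious benefit.

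**Working it through.** **Inputs from Section 8:** 15 completers, true reduction 4.8 s (36.7 to 31.9 s), SD of paired differences 6.6 s, two-sided alpha 0.05, Wilcoxon signed rank test. **Assumption:** a scan that follows CPET is shifted by c = 0 to 3 s. The documents give no value.

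**The plan's own figure.** n = (6.6 × (1.960 + 0.842) / 4.8)² = 14.84, rounded up to 15, with 80.4% power by the normal approximation. So 15 is reproduced. An exact paired t-test at n = 15 has 74.5% power. The exact Wilcoxon test (reject if the smaller rank sum is 25 or less, size 4.8%) has about 72% by simulation. That 72% is the starting point below; its distance from 80% is a separate matter and adds nothing to this point.

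**Formulas.** Let p0 and p12 be the shares of subjects scanned after CPET at baseline and week 12.

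- Bias in the mean change = c × (p12 − p0).
- Added variance, if order is chosen independently at each time point = c² × [p0(1 − p0) + p12(1 − p12)].
- Same order and same gap in every subject: c cancels, bias 0, SD stays 6.6 s, power stays about 72%.
- Same order but different gap: what remains is the difference between the two carry-overs.

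**Values at c = 3 s:**

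- Independent 50/50 at both time points: bias 0; variance 6.6² + 9 × 0.50 = 48.06, SD 6.93 s.
- Independent 20/20 at both: bias 0; variance 43.56 + 9 × 0.32 = 46.44, SD 6.81 s.
- Every subject reverses order, half each way: bias 0; variance 43.56 + 9 = 52.56, SD 7.25 s.
- 3 of 15 after CPET at week 12 only: bias 3 × 0.2 = 0.6 s.
- 0% at baseline, 50% at week 12: bias 3 × 0.5 = 1.5 s.

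**Simulated Wilcoxon results** (normal differences, 300,000 trials per cell). Power is for a true 4.8 s reduction with c lengthening recovery. False positives are two-sided, with no true effect and c shortening recovery.

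| Pattern | Power at c = 1 / 2 / 3 s | False positives at c = 1 / 2 / 3 s |
|---|---|---|
| Matched order and gap | 72 / 72 / 72% | 4.8% throughout |
| Independent, 20/20 | 72 / 71 / 69% | about 4.8% throughout |
| Independent, 50/50 | 72 / 70 / 68% | about 4.8% throughout |
| All reverse, half each way | 71 / 68 / 64% | 4.8% throughout |
| 3 of 15 after CPET, week 12 only | 68 / 64 / 59% | 4.9 / 5.2 / 5.6% |
| 0% baseline, 50% week 12 | 62 / 51 / 40% | 6 / 8 / 12% |

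**The case against.** The strongest reply is that the documents contain neither the mechanism nor the imbalance.

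- **Mechanism.** No section says that CPET changes a later scan. The scan uses two minutes of one-foot exercise at 30% of maximum in one leg muscle, and at week 12 at least a day separates the tests. The 0 to 3 s range is an assumption, and its upper end is 3 / 4.8 = 63% of the effect the study is sized to detect. This stands, and it makes the point conditional.
- **Imbalance.** Note 4 gives the same freedom at both time points. The text leans towards MRS first at both: Visit 2 lists MRS and not CPET, and the table marks week-12 research blood, which the visit text ties to CPET, only at Visit 8. With the same mix at both time points there is no bias and little loss of power. This also stands. A reader might infer from the last row of the table that the trial faces 40% power or 12% false positives. The documents do not support that; it is a chosen worst case.
- **Spacing.** A reader might infer that the plan spaces the tests differently at the two time points. The table does not: both visit pairs are one to two days apart. No section plans same-day testing at baseline; it is simply not excluded there, whereas the week-12 text does separate the tests. The longer window in the Visit 8 heading is an inconsistency of one day.
- **Analysis.** It would be unfair to fault the signed rank test for lacking an order term, which 15 pairs could hardly support. The remedy belongs in the schedule.

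What survives is that the lean towards MRS first is not a rule, the other order is expressly kept open, and no section asks for order or gap to be matched within subject.

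**Conclusion.** The point holds as a minor, conditional one. The schedule leaves the order free at both time points and the gap free at baseline, and an uncontrolled paired endpoint has no protection if either differs within a subject.

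Under an assumed carry-over of up to 3 s, with n = 15 and SD 6.6 s, the size depends on the pattern. It is zero if order and gap are matched. With the same mix at both time points, there is no bias and a loss of about 2 to 4 points of power. If every subject reverses, the loss is about 8 points (72% to 64%). Bias arises only when the mix or the gap differs systematically; 3 of 15 subjects at week 12 alone would take power to 59% at 3 s.

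A reader might infer that the primary result will be biased by CPET. The documents do not show that a carry-over exists or that the order will differ between time points, so that conclusion is not available.

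**What to change.** Amend note 4 and the text of Visits 2, 3, 7B and 8 so that each subject's baseline order and gap of MRS and CPET are repeated at week 12, with the two tests on separate visits both times.

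The simplest way is MRS first at both time points: MRS at Visits 2 and 7B, CPET at Visits 3 and 8. This follows the existing lean of the text and makes both scans comparable with the week-16 scan, which has no CPET near it. Supplementation begins in the evening after Visit 3 and stops at Visit 8, so both baseline tests still precede it and the change of order requires no change to dosing.

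Record the order, dates and times of both tests at each time point. Reconcile the Visit 8 window between the schedule table (one to two days) and the visit heading (one to three days).

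The cost is protocol wording, one recorded item and slightly less scheduling flexibility. No visits, scans or subjects are added, and the sample size does not change.
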